
Study Objectives

Primary Objectives

The **primary objective** of this study is to evaluate the current management approach with “intermediate” or “therapeutic” doses of tinzaparin for thromboprophylaxis in hospitalized patients, non on ICU organ support, with confirmed COVID-19.

- Evaluate incidence of thrombotic events
- Evaluate incidence of bleeding events

Secondary Objectives

The **secondary objective** is to

- ✓ Examine the course of illness of COVID-19 via measure of clinical improvement and/or survival, assessed at pre-specified time points post admission

Patients demographic & somatometric data, medical history (thrombosis & bleedings related history, co-morbidities, chronic use of medications, results of laboratory tests etc.), clinical parameters, anticoagulant prophylaxis dose & duration, efficacy (thrombosis events), safety (bleedings), imaging and laboratory tests results and information about other supportive treatment will be recorded; more than one outcomes could be recorded.

Based on analysis of collected data, **we'll examine correlations between thromboprophylaxis approach, patients' profiles and clinical outcomes.**

Study Endpoints

Primary Endpoints

- **Incidence of thrombotic events** (total & per type e.g. PE, DVT, symptomatic, incidental, proximal, distant etc.)
- **Incidence of bleeding events** (total & per type e.g. Major, CRNMB and minor)

Secondary Endpoint

- **World Health Organization (WHO) progression scale** (range from 0 (healthy) to 10 (death); values below or equal to 5 correspond to the absence of any oxygen supply beside nasal or facial mask)
- **Length of hospital stay (days)**

Study Design

This is a retrospective phase IV, observational, non-interventional cohort study that aims to collect data regarding thromboprophylaxis management in high thrombotic risk hospitalized, non on ICU, patients with COVID-19 pneumonia. Specifically, we will collect retrospectively data for patients received thromboprophylaxis with tinzaparin, according to current clinical practice, during hospitalization, for one year before the study initiation date, to evaluate safety and efficacy of thromboprophylaxis and to examine possible associations of

patients' profiles with thrombotic and bleeding events and the course of illness in this cohort of patients.

We will collect data retrospectively in paper CRFs, recorded from the treating physicians.

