Additionally, we will assess the association of a panel of laboratory and clinical parameters representing an inflammatory and hemostatic state with VTE and bleeding events and clinical outcomes.

Institutional Review Board will approve the study.

Basic/common markers/parameters

- ✓ *D-Dimers*
- ✓ *C-reactive protein (CRP)*
- ✓ *hemoglobin*
- ✓ *platelets count*
- ✓ *ferritin*
- ✓ *fibrinogen*
- ✓ *SpO₂ in FiO₂ 21%*

In all cases, laboratory and clinical parameters will be collected at 3 time points: at admission/baseline, after one week and at discharge.

Subject Population

Key criteria for Inclusion and Exclusion

Inclusion Criteria

1. Patients admitted to hospital with COVID-19, PCR+ SARS-CoV-2 infection (from any specimen) administered thromboprophylaxis with tinzaparin in intermediate or therapeutic dose
2. Age \geq 18 years
3. Signed informed consent

Exclusion Criteria

1. Patients admitted to ICU with COVID-19, PCR+ SARS-CoV-2 infection (from any specimen)
 2. Age < 18 years
 3. Pregnancy
 4. Current diagnosis or suspicion of pulmonary thromboembolism or deep vein thrombosis
 5. Progression to death was imminent and inevitable within 24 hours from the admission, irrespective of the provision of treatments
 6. Not signed informed consent
-

Study Phases**Screening**

(1) Screening: screening patient files for eligibility, obtaining consent, If eligible

All the data will be gathered from medical records by chart review of the individual patients in a retrospective fashion. There will no direct patient interaction in the study.

Data collection

- Demographic data collection (Gender, Date of birth, Weight, Height, etc.)
- Medical history & pathologic features (Thrombosis & bleedings related history, risk factors, recent surgery, co-morbidities, chronic use of medications, results of laboratory tests, clinical parameters etc.)
- Anti-coagulant administration data
- Thrombotic & bleeding events during course of hospitalization
- Other adverse events related to anticoagulation
- Clinical improvement and/or survival during hospitalization

Timepoints of evaluation

Data of Covid-19 pneumonia patients retrospectively enrolled in the study will be evaluated on a regular basis following the Baseline Visit;

Visit 1 – Baseline, at admission;

Visit 2 - will be after 1 week \pm 2 days

Visit 3 - will be by at discharge from hospital

Statistical analysis & report**Statistical analysis****Statistical and Analytic Plan**

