Descriptional statistical analysis will be performed for all study data along with epidemiology methods. Categorical data will be analyzed using the *chi-square* and *Fisher exact test*. Continuous variables will be reported as mean and standard deviations (SD) and will be analyzed using the *t-test* analysis. An unadjusted odds ratio (OR) will be calculated using a *Cochran-Mantel-Haenszel test*. To determine the impact of potential effect modifiers a *logistic regression model* will be used to calculate the adjusted odds ratio. For more complex correlations (i.e. inferential statistics) we will use, among other methods, *chi-square* or *Fisher exact tests*, *ANOVA*, *Mann-Whitney U tests* and *t-tests*, according to the data properties and in order to evaluate the relationships between different patient and disease characteristics with the primary and secondary study outcomes, such as:

- ✓ *Number of patients enrolled*
- ✓ *Co-morbidities*
- ✓ *Thrombosis risk factors*
- ✓ *Laboratory parameters*
- ✓ *Clinical parameters*
- ✓ *Type and duration of thromboprophylaxis therapy*
- ✓ *Therapy outcomes*
- ✓ *Thromboprophylaxis related complications*

and to present them, accordingly.

Due to the fact that this is an observational study the results of all correlations will be carefully discussed and will be used only to assess hypotheses.

Finally and depending on the collected data multivariate analysis may be performed in order to reveal confounding factors.

Clinical Study Report (CSR)

Analyzed parameters will be presented with standards statistical measures (mean values, median values, ranges, quartiles, percentages etc.) and the results will be presented accordingly into tables and informative plots.

A p-value of less than 0.05 will be considered statistically significant and all values will be reported with a 95% confidence interval (CI).

Study Registration

Study will be registered in

NIH, U.S. National Library of Medicine, Clinical Trials database of privately and publicly funded clinical studies, <https://clinicaltrials.gov/ct2/home>

Efficacy Evaluations

- ***Symptomatic/Suspected vein thromboembolism, including pulmonary embolism and deep vein thrombosis***

Confirmation of symptomatic PE requires symptoms of PE and one of the following findings

1. *A (new) intraluminal filling defect in (sub) segmental or more proximal branches on spiral CT scan or on MRI scan;*

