2. *A (new) intraluminal filling defect or an extension of an existing defect or a new sudden cut-off of vessels on the pulmonary angiogram;*
3. *An inconclusive lung scan accompanied by documentation of (new) DVT in the lower extremities e.g., by compression ultrasound or venography.*

Confirmation of symptomatic DVT requires symptoms of DVT and:

1. *A (new) non-compressible venous segment on ultrasonography
Incidental PE with one of the following:*
2. *A (new) intra-luminal filling defect on CT scan, MRI scan, or pulmonary angiogram;*
3. *An inconclusive lung scan accompanied by documentation of (new) DVT in the lower extremities e.g., by compression ultrasound or venography.*

Fatal PE is:

1. *PE based on objective diagnostic testing or autopsy or*
-

-
2. *Death not attributed to a documented cause and for which DVT/PE cannot be ruled out*

Incidental DVT with the following finding:

Confirmation of incidental DVT requires inconclusive or no- symptoms of DVT and:

1. *A (new) non-compressible venous segment on ultrasonography*

**Safety Evaluations
(with regards to
anticoagulation)**

- **Major, Clinically Relevant Non-Major Bleeding (CRNMB), and minor bleeding**

Major bleeding will be defined as overt bleeding associated with: a fall in hemoglobin of 2 g/dL or more, or leading to a transfusion, or bleeding that occurs in a critical site or contributing to death.

- **Bleeding in a critical area or organ such as:**

- ✓ *Retroperitoneal*
- ✓ *Intracranial*
- ✓ *Intraocular*
- ✓ *Intraspinal*
- ✓ *Intra-articular*
- ✓ *Pericardial*
- ✓ *Intramuscular with compartment syndrome*

- **A clinically overt bleeding event**

- ✓ *that is associated with a fall in hemoglobin of 2.0 g/dL (>1.24 mMol/L) or more, or*
- ✓ *leading to a transfusion of ≥ 2 units of packed red blood cells or whole blood*

- **Bleeding contributing to death**

- Other **clinically relevant non-major bleedings (CRNMB)** will be defined as overt bleeding not meeting the criteria for major bleeding but associated with medical intervention, unscheduled contact (visit or telephone call) with a physician, (temporary) cessation of study treatment, or associated with discomfort for the patient such as pain, or impairment of activities of daily life.
 - All other bleeding events will be classified as **minor**
-

- **World Health Organization (WHO) progression scale**

Patient State	Descriptor	Score
Uninfected	Uninfected; no viral RNA detected	0

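### A death with no recorded cause counts as fatal PE when DVT/PE is not excluded, so total thrombotic incidence can mix confirmed VTE with undocumented deaths

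*Combined protocol and SAP*

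**What the plan says.** Study Endpoints makes "incidence of thrombotic events" a primary endpoint, to be given as "total & per type e.g. PE, DVT, symptomatic, incidental, proximal, distant etc". The list is open and does not name fatal PE.

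Efficacy Evaluations defines the venous event types. For symptomatic PE, "Confirmation of symptomatic PE requires symptoms of PE and one of the following findings"; the listed findings are imaging results, or an inconclusive lung scan backed by documented DVT. Symptomatic DVT, incidental PE and incidental DVT likewise each need an objective finding.

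Fatal PE has two limbs, either of which is enough:

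- Limb 1: "PE based on objective diagnostic testing or autopsy or"
- Limb 2: "Death not attributed to a documented cause and for which DVT/PE cannot be ruled out"

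Under Safety Evaluations, one criterion for major bleeding is "Bleeding contributing to death".

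On data sources, Study Phases says "All the data will be gathered from medical records by chart review of the individual patients in a retrospective fashion", and Study Design says "We will collect data retrospectively in paper CRFs, recorded from the treating physicians". The synopsis describes no adjudication of events, no standard for deciding that VTE has not been excluded, and no analysis that sets limb 2 deaths apart.

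**The concern.** Limb 2 is the only defined venous event that can be met without any sign of a clot. It is met by two absences: no cause of death in the chart, and nothing in the chart that excludes DVT/PE. In a retrospective chart review, both depend partly on how fully the death was worked up and written down.

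Two results are exposed. The first is the total thrombotic incidence. Every enrolled patient received tinzaparin at intermediate or therapeutic dose, so there is no untreated or lower-dose group. The absolute incidence is the main result, and no control arm carries the same misclassification. The second is the planned association of D-dimer, CRP, ferritin, oxygen saturation and other markers with VTE. Death is also score 10 on the WHO scale, a secondary endpoint. A limb 2 death therefore counts in both outcomes, and a predictor of COVID-19 death can appear as a predictor of thrombosis.

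A separate, smaller point concerns limb 1. It does not say that the PE caused or contributed to the death, although the bleeding definition does use such wording.

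**Working it through.** The plan states no sample size, thrombosis rate or mortality for non-ICU patients, so it has no figure to reproduce. The 25% to 40% mortality in Study Rationale refers to patients needing organ support on the ICU. ICU patients are excluded, so that figure cannot be used here.

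**Step 1. The definitions side by side.**

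| Event | Objective finding needed? | Link to death stated? |
|---|---|---|
| Symptomatic PE, symptomatic DVT | Yes | Not applicable |
| Incidental PE, incidental DVT | Yes | Not applicable |
| Fatal PE, limb 1 | Yes (testing or autopsy) | No |
| Fatal PE, limb 2 | No | The death is itself the event |
| Major bleeding, death criterion | Overt bleeding | Yes (contributed) |

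**Step 2. What each limb does to the total.** A limb 1 case is an objectively shown PE, so it is a thrombotic event whether or not it caused the death. Adding a causal condition moves it between fatal and non-fatal PE and leaves the total unchanged. Autopsy is named only in limb 1, so this holds provided a PE found at autopsy stays a confirmed PE when another cause of death is recorded. A limb 2 case has no other route into the total. Only limb 2 can add events without evidence of thrombosis.

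**Step 3. Illustration of size. All inputs are assumptions.** Let c be the proportion of enrolled patients with confirmed VTE, d the proportion who die in hospital without confirmed VTE, and u the share of those deaths that meet limb 2.

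- Total incidence = c + d × u
- Share of events from limb 2 = d × u / (c + d × u)

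With c = 3% and d = 5%:

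| u | d × u | Total | Share from limb 2 |
|---|---|---|---|
| 0 | 0 | 3.0% | 0% |
| 10% | 0.5% | 3.5% | 0.5/3.5 = 14% |
| 20% | 1.0% | 4.0% | 1.0/4.0 = 25% |
| 50% | 2.5% | 5.5% | 2.5/5.5 = 45% |

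Over a wider grid (c = 1%, 3%, 5%; d = 2%, 5%, 10%; u = 0, 10%, 20%, 50%), the share runs from 0% to 83%. The upper end is c = 1%, d = 10%, u = 50%: 5/(1 + 5) = 83%. A mild case is c = 5%, d = 2%, u = 10%: 0.2/5.2 = 4%. The range shows that the effect depends almost wholly on quantities the plan does not give.

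**The case against.** The strongest reply is that limb 2 may be almost empty. Signed consent is required and no provision is stated for patients who died. ICU admissions are excluded, and so are patients whose death was judged imminent within 24 hours of admission. Every patient is PCR-positive, so many charts may record COVID-19 as the cause of death, which takes the death out of limb 2. This stands: the effect may be near zero, and no percentage should be presented as the expected bias.

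A reader might infer that every unexplained death is counted. The text does not say so. Limb 2 also requires that DVT/PE has not been excluded, and imaging results are among the data to be recorded, so some deaths could be screened out. A reader might also infer that limb 1 inflates the total; Step 2 shows that it does not. It can further be said that the heading of the fatal PE definition itself implies a link to the death. That is a fair reading, so limb 1 needs a clarification of wording. Nor do the documents show that hospitals differ in how they certify deaths; such variation is possible but not described.

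There is partial mitigation. Incidence is reported per type, death is captured separately on the WHO scale, and the Statistical and Analytic Plan limits correlations to assessing hypotheses. But a single fatal PE line would mix the two limbs, so a reader of the report could not recover the confirmed total.

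Finally, counting such deaths guards against missing true undiagnosed fatal PE. That is a reason to show both totals rather than simply to drop limb 2.

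**Conclusion.** The point holds for limb 2. A death can be counted as fatal PE with no positive evidence of thrombosis, and nothing in the plan separates such deaths from confirmed VTE in the primary incidence or in the marker associations. That they enter the total is a strong inference from the endpoint wording and from where fatal PE is defined; the plan does not state it outright. The contrast with other events covers the defined venous types only, since the synopsis gives no criterion for arterial thrombosis.

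The size cannot be determined from the documents. The 14% to 25% share at c = 3%, d = 5% and u = 10% to 20% is an illustration, and zero lies within the plausible range. The documents do not support a claim that the reported incidence will be materially inflated. They support a narrower one: as planned, a reader could not tell whether it was.

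The missing causal wording in limb 1 is a separate and lesser matter that affects the fatal PE subtype alone.

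**What to change.** 1. Report fatal PE on two lines, one for each limb, and have the CRF record which limb was met.
2. Give the total thrombotic incidence, with its 95% CI, both with and without limb 2 deaths, and state whether fatal PE belongs to the total.
3. Run the association analyses for thrombotic events both ways.
4. In limb 1, count a confirmed PE as fatal only when the record attributes the death to PE. Otherwise keep it as a non-fatal PE, including when it was found at autopsy.

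The cost is one extra table row, a definition edit and a repeated analysis. The total without limb 2 may miss some true undiagnosed fatal PE, which the total with limb 2 still shows. The limb 1 change makes the fatal subtype depend on what the chart says about the cause of death, but the total does not move.
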